9.5.3 Mosquito Dissection

Mosquitoes are knocked down and then transferred into a Petri dish containing a slightly wet paper towel. Under a dissecting scope and on a slide, each individual specimen is placed in a drop mercurochrome solution. The midgut is pulled and covered with a coverslip. The oocysts are detected under a light microscope. The presence of oocyst and oocyst counts for each specimen will be recorded. A mosquito will be considered positive if ≥ 1 oocyst is present.

If needed, the head and thorax of the mosquitoes may be processed for ELISA to detect sporozoites and for PCR to identify species and molecular form of the mosquito.

Additional details on mosquito rearing, feeds, and dissection will be described in study SOPs.

9.6 Schistosomiasis and Helminthes Infection Testing

Endemic helminthes infections in sub-Saharan Africa, such as helminth and schistosomiasis infections, are known to elicit a wide range of immunomodulating responses and may impact the efficacy of vaccinations.³⁶⁻³⁸ This potential impact of co-infections on vaccine immunogenicity will depend on the prevalence of local helminth and schistosomiasis infections. With the introduction of phase 1 malaria trials into Africa, consideration and initial exploration into the existence of co-infections in vaccinees and the impact on vaccine efficacy and immunogenicity needs to be explored.

To assess the impact of co-infections on immune responses, schistosomiasis testing (may include urine microscopic examination for *S. haematobium* and stool PCR for *S. mansoni*; urine antigen detection) and helminthes testing³⁹ (stool PCR for 8 common gastrointestinal pathogens) will be

completed on Study Day 0 in Arms 2c, 2d, 4c only. Given these tests are run for research purposes and retrospectively, if these results are available prior to the final study visit and parasites are detected, and recommended, subjects will be treated with standard treatment and continued in the study.

9.7 Other Laboratory Assays

If there is adequate remaining blood sample available to fulfill the laboratory objectives, other laboratory assays may be performed as follows:

- Malaria rapid diagnostic tests (RDTs) may be used for clinical diagnosis purposes.
- qPCR may be used to detect gametocytes using whole blood collected on the day of DSF and/or positive blood smears.
- Filter paper filled with whole blood, whole blood, or mosquitoes may be used to determine parasite genotype.
- Antibodies against sporozoite, pre-erythrocytic, blood, and sexual stages may be determined by ELISA.
- Mosquito species and molecular forms may be identified by qPCR..⁴⁰
- Hemoglobin variants (Hgb C, S, alpha thalassemia), glucose-6-phosphate dehydrogenase deficiency, and ABO blood group/Rhesus factor may be assessed using high-performance liquid chromatography and/or other standard methodology.
- Human leukocyte antigen genotypes may be evaluated for genetic polymorphisms, allelic and antigenic diversity.
- B cell receptor/antibody genes may be sequenced to explore the antibody repertoire of functional antibody responses.
- Cytokine levels may be evaluated during vaccination and following vaccination.
- Direct membrane feeding assays may be completed following Vaccination #3 to compare to SMFA and DSF results.

Study physicians may ask for additional laboratory exams related to subject care.

10 Research Use of Stored Human Samples, Specimens, or Data

Intended Use: Samples and data collected under this protocol will be used to study malaria and related diseases and possible adverse reactions to vaccination. Genetic testing may be performed in accordance with the genetic testing information that is included in the study informed consent.

Storage: Access to stored research samples will be limited using either a locked room or a locked freezer. Temporary storage of samples collected in Mali, prior to shipment to LMIV, may occur at the Core Immunology Laboratory or the MRTC CAP laboratory. Samples will be stored at the LMIV in Rockville, MD or at LMIV's designated repository, Thermo Scientific,

Rockville, MD, with the exception of retention specimens which may be kept at the MRTC in Mali for quality control. Samples and data will be stored using codes assigned by the investigators or their designees. Data will be kept in password-protected computers. Only investigators or their designees will have access to the samples and data.

Tracking: Samples will be tracked using a sample-tracking software program, e.g., Freezerworks.

Disposition at the Completion of the Protocol: In the future, other investigators (both at the NIH and outside) may wish to study these samples and/or data. In that case, IRB approval must be sought prior to any sharing of samples. Any clinical information shared about the sample with or without patient identifiers would similarly require prior IRB approval.

At the completion of the protocol (termination), samples and data will either be destroyed or, after IRB and FMPOS EC approval, transferred to another existing protocol.

Reporting the Loss or Destruction of Samples/Specimens/Data to the IRB: Any loss or unanticipated destruction of samples (for example, due to freezer malfunction) or data (for example, misplacing a printout of data with identifiers) that meets the definition of Protocol Deviation and/or compromises the scientific integrity of the data collected for the study, will be reported to the NIH IRB and FMPOS EC.

Consent to allow long term storage of study samples is a part of the inclusion criteria for this study. However, if a subject decides following enrollment not to have their samples stored the Principal Investigator or designee will destroy all known remaining samples and report this destruction to the subject and the NIH IRB and FMPOS EC. This decision will not affect the subject's continued participation in this protocol or any other protocols supported by the NIH.

11 Data Sharing Plan

In NIH's and MRTC's view, all data should be considered for data sharing. Data should be made as widely and freely available as possible while safeguarding the privacy of subjects, and protecting confidential and proprietary data. We recognize that the public dissemination of our scientific results can facilitate the creation of collaborative efforts with domestic and international collaborators. Furthermore, we recognize that the proposed project may result in novel ideas for new methods, technologies, and data that could benefit the entire research community. Therefore, final research data will be shared openly and timely in accordance with the most recent NIH guidelines (http://grants.nih.gov/grants/policy/data_sharing/) while being mindful that the confidentiality and privacy of participants in research must be protected at all times. Timelines for distribution of data will vary depending on any required restrictions in accordance with federal and/or institutional policies and guidelines. In general we expect de-identified data will be available through NIH-funded or approved public repository, speaking

engagements and publications, presentations at scientific symposia and seminars. Effort will be made to publish our research findings in scientific journals. All final peer-reviewed manuscripts that arise from this proposal will be submitted to the digital archive PubMed Central. For tools, reagents, data and model organisms generated by the proposed study, pending third parties rights, LMIV/MRTC will transfer materials to outside researchers in both the private and public sectors under a Material Transfer Agreement or Research Collaboration Agreement. Discussions of unpublished ELISA and SMFA data from this trial with collaborators will be conducted under a Confidential Disclosure Agreement.

12 Assessment of Safety

12.1 Documenting, Recording, and Reporting Adverse Events

At each contact with the subject, information regarding adverse events will be elicited by appropriate questioning and examinations and will be:

- immediately documented in the subject's medical record/source document,
- recorded on the Adverse Event Case Report Form (AE CRF) or electronic database, and
- reported as outlined below (e.g., IND Sponsor, IRB, FDA).

A study clinician will be available during the study period and will be available to the study subjects at all times. Should a subject call a study clinician to report an AE, it will be discussed with the PI and documented, recorded, and reported appropriately.

12.2 Definitions

Adverse Event (AE)

An adverse event is any untoward or unfavorable medical occurrence in a human subject, including any abnormal sign (e.g., abnormal physical exam or laboratory finding), symptom, or disease, temporally associated with the subject's participation in the research, whether or not considered related to the research.

Adverse Reaction (AR)

An adverse event that is caused by an investigational agent (drug or biologic).

Suspected Adverse Reaction (SAR)

An adverse event for which there is a reasonable possibility that the investigational agent caused the adverse event. 'Reasonable possibility' means that there is evidence to suggest a causal relationship between the drug and the adverse event. A suspected adverse reaction implies a lesser degree of certainty about causality than adverse reaction which implies a high degree of certainty.

Serious Adverse Event (SAE)

A Serious Adverse Event (SAE) is defined as an AE that results in any of the following outcomes:

- death
- a life threatening (i.e., an immediate threat to life) event
- an inpatient hospitalization or prolongation of an existing hospitalization
- a persistent or significant incapacity or substantial disruption of the ability to conduct normal life functions
- a congenital anomaly/birth defect
- a medically important event*

* Medical and scientific judgment will be exercised in deciding whether expedited reporting is appropriate in other situations, such as important medical events that may not be immediately life threatening or result in death or result in hospitalization but may jeopardize the subject or may require intervention to prevent one of the other outcomes listed above.

Unexpected Adverse Event

An AE is considered unexpected if it is not listed in the Investigator's Brochure or Package Insert (for marketed products) or is not listed at the specificity or severity that has been observed. It is the responsibility of the IND Sponsor to make this determination.

Serious and Unexpected Suspected Adverse Reaction (SUSAR)

A SUSAR is a Suspected Adverse Reaction that is both serious and unexpected.

Unanticipated Problem (UP)

An Unanticipated Problem (UP) is any event, incident, experience, or outcome that is

1. unexpected in terms of nature, severity, or frequency in relation to
 - a. the research risks that are described in the IRB-approved research protocol and informed consent document, Investigator's Brochure, or other study documents; and
 - b. the characteristics of the subject population being studied; and
2. possibly, probably, or definitely related to participation in the research; and
3. places subjects or others at a greater risk of harm (including physical, psychological, economic, or social harm) than was previously known or recognized. (Per the IND Sponsor, an AE with a serious outcome will be considered increased risk.)

Serious Unanticipated Problem (UP)

A UP that meets the definition of a Serious Adverse Event or compromises the safety, welfare or rights of subjects or others.

Unanticipated Problem that is not an Adverse Event (UPnonAE)

An unanticipated problem that does not fit the definition of an adverse event, but which may, in the opinion of the investigator, involve risk to the subject, affect others in the research study, or significantly impact the integrity of research data. Such events would be considered a non-serious UP. For example, we will report occurrences of breaches of confidentiality, accidental destruction of study records, or unaccounted-for study drug.

New Onset of Chronic Illness (NOCI)

The new onset of chronic illness is defined as a diagnosis of a new medical condition that is chronic in nature, including those potentially controllable by medication (e.g., diabetes, asthma). Any NOCI will be recorded in the same manner as unsolicited AEs.

12.3 Investigator Assessment of Adverse Events

If a diagnosis is clinically evident (or subsequently determined), the diagnosis rather than the individual signs and symptoms or lab abnormalities will be recorded as the AE.

All solicited (see [Table 14](#) below) and unsolicited AEs will be recorded through Day 7 after each vaccination, including injection site reactions, or until resolved. Adverse reactions related to direct skin feeds will be recorded until Day 7 after feeds or until resolved. After that period only unsolicited AEs (including symptomatic malaria), SAEs, UPs, and NOCIs will be recorded. Note that a positive blood smear without associated clinical symptoms will not be reported as an AE.

Table 14: Solicited Adverse Events

Systemic adverse events
Fever (temperature ≥ 38.0 °C)
Headache
Nausea/Vomiting
Diarrhea
Abdominal pain
Fatigue
Myalgia
Arthralgia
Urticaria
Laboratory adverse events
Hemoglobin – decreased hemoglobin
WBC – leukopenia, leukocytosis
ANC/AGC – decreased neutrophil/granulocyte count

Platelet count – thrombocytopenia
ALT – increased ALT
Creatinine (Cr) – increased Cr
Local reactogenicity
Injection pain/tenderness
Injection erythema/redness
Injection swelling
Injection induration
Injection pruritus
Limitation of arm movement

Additional laboratory abnormalities other than those specified as safety labs in the protocol should be reported as adverse events if they require intervention. Interventions include, but are not limited to, discontinuation of treatment, dose reduction/delay, additional assessments, or concomitant treatment. In addition, any medically important laboratory abnormality may be reported as an adverse event at the discretion of the investigator. This could include a laboratory result for which there is no intervention but the abnormal value suggests a disease or organ toxicity. In addition, similar to solicited AEs, all laboratory AEs as defined in [Appendix D](#), will be collected and graded through 7 days after each vaccination or until resolved.

The investigator will evaluate all AEs with respect to Seriousness (criteria listed above), Severity (intensity or grade), and Causality (relationship to study agent and relationship to research) according to the following guidelines.

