3.1.1.1 Safety of Pfs25H-EPA/Alhydrogel® in Healthy US Adults

[figure not shown]
Vaccinations were well-tolerated, with minimal local and systemic reactogenicity.^{15,23} There was an increase in the percentage of subjects reporting solicited adverse events (AEs) with each escalating dose, with AEs diminishing with each subsequent dose of vaccine given. No subjects were withdrawn due to related adverse events. A single serious adverse event (SAE) occurred during the course of the study that was unrelated to the vaccine. These findings are summarized in [Figure 4](#).

Figure 4: Related Local Injection Site Reactogenicity and Systemic Adverse Events.

All injection site reactogenicity was deemed related to Pfs25H-EPA/Alhydrogel®. Clinical solicited (A-C) adverse events after each vaccination with each dose group are reported in individual graphs: Group 1a (A), 1b (B) and Group 2 (C). All adverse events were mild except when indicated as moderate.

[figure not shown]
All laboratory adverse events (related and unrelated) are shown in [Figure 5](#). While several subjects experienced anemia after vaccination, the majority of these events were judged to be unrelated to vaccination, either because these subjects had low, but normal, hemoglobin levels at baseline (day of first vaccination) or because of an alternate explanation (e.g., blood donation or previously undisclosed history of anemia). An examination of trends in hematologic parameters does not show any pattern related to timing of vaccinations.¹⁵

Figure 5: Laboratory Adverse Events

Laboratory (A-C) adverse events after each vaccination with each dose group are reported in individual graphs: Group 1a (A), 1b (B) and Group 2 (C). All adverse events were mild except when indicated as moderate. All neutropenia events occurred in the same subject. All hematuria occurred during menses. All leukopenia events occurred in the same subject. All laboratory adverse events except for a portion of the decreased hemoglobin (n=10) were found by the PI to be unrelated to Pfs25H-EPA/Alhydrogel[®]

[figure not shown]

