5.2 Study Endpoints

5.2.1 Primary Endpoint

- Incidence of local and systemic AEs and SAEs in Malian adults. (All arms)
- Incidence of local and systemic AEs and SAEs in Malian adults. (Arms 2c, 2d, 4c)

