6.5 Exclusion Criteria (Initial enrollment and Re-enrollment)

A subject will be excluded from participating in this trial if any one of the following criteria is fulfilled:

1. Pregnancy as determined by a positive urine or serum human choriogonadotropin (β -hCG) test (*if female*). (*Arms 2c, 2d, 4c only for re-enrollment*)

NOTE: Pregnancy is also a criteria for discontinuation of any further dosing or non-safety related interventions for that subject.
2. Currently breast-feeding (*if female*). (*Arms 2c, 2d, 4c only for re-enrollment*)

3. Behavioral, cognitive, or psychiatric disease that in the opinion of the investigator affects the ability of the participant to understand and comply with the study protocol.
4. Hemoglobin, WBC, absolute neutrophils, and platelets outside the local laboratory-defined limits of normal (subjects may be included at the investigator's discretion for 'not clinically significant' values outside of normal range and \leq Grade 1). (*Arms 2c, 2d, 4c only for re-enrollment*)
5. Alanine transaminase (ALT) or creatinine (Cr) level above the local laboratory-defined upper limit of normal (subjects may be included at the investigator's discretion for 'not clinically significant' values outside of normal range and \leq Grade 1). (*Arms 2c, 2d, 4c only for re-enrollment*)
6. Infected with human immunodeficiency virus (HIV), hepatitis C virus (HCV), or hepatitis B (HBV). (*Arms 2c, 2d, 4c only for re-enrollment*)
7. Evidence of clinically significant neurologic, cardiac, pulmonary, hepatic, endocrine, rheumatologic, autoimmune, hematological, oncologic, or renal disease by history, physical examination, and/or laboratory studies including urinalysis.
8. History of receiving any investigational product within the past 30 days.
9. Participation or planned participation in a clinical trial with an investigational product prior to completion of the follow up visit 28 days following last vaccination OR planned participation in an investigational vaccine study until the last required protocol visit
10. Subject has had medical, occupational, or family problems as a result of alcohol or illicit drug use during the past 12 months.
11. History of a severe allergic reaction or anaphylaxis. (*Arms 2c, 2d, 4c only for re-enrollment*)

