Hemoglobin (Female) gm/dL	8.0 – 9.0	7.0 – 7.9	6.0 – 6.9	< 6 and /or requiring transfusion
WBC Increase – 10 ³ /μL	11.5 – 15.0	15.1 – 20.0	20.1 – 25.0	> 25.0
WBC Decrease - 10 ³ /μL	2.5 – 3.3	1.5 – 2.4	1.0 – 1.4	< 1.0
Neutrophil/Granulocyte Decrease ³ - 10 ³ /μL	0.80 – 1.00	0.50 – 0.79	< 0.50	< 0.50 with fever
Platelets Decreased – 10 ³ /μL	100 – 115	70 – 99	25 – 69	< 25
Creatinine (Male) μmol/L	132.60 – 159.11	159.12 – 185.63	185.64 – 221.00	> 221.00 and requires dialysis
Creatinine (Female) μmol/L	97.42 – 116.94	116.95 – 136.44	136.45 – 162.43	> 162.43 and requires dialysis
Liver Function Tests – ALT U/L	46.0 – 106.5	106.6 – 209.0	209.1 – 410.0	> 410.0

¹ The laboratory values provided in the table are taken from the FDA Guidance for Industry “Toxicity Grading Scale for Healthy Adults and Adolescent Volunteers Enrolled in Preventive Vaccine Clinical Trials” dated September 2007. The laboratory values provided in the referenced tables serve as guidelines and have been adapted for institutional normal parameters (see below). Institutional normal reference ranges should be provided to demonstrate that they are appropriate.

² The clinical signs or symptoms associated with laboratory abnormalities might result in characterization of the laboratory abnormalities as Potentially Life Threatening (Grade 4). For example, a low sodium value that falls within a grade 3 parameter should be recorded as a grade 4 hyponatremia event if the subject had a new seizure associated with the low sodium value.

³ Note, neutropenias are graded and followed, but based on previous experience in African populations, should be interpreted with caution since lower values are more frequently observed in people of African descent ^{46,47}.

Mali Adult: Institutional Normal Parameters**Chemistry**

Serum¹	Reference Range
Creatinine (Female) - $\mu\text{mol/L}$	< 72
Creatinine (Male) - $\mu\text{mol/L}$	48 – 98
ALT – U/L	< 41

¹The laboratory values provided in the table are based on Bancoumana, Malian adults (age 18-45 years old)

Hematology

Hematology¹	Reference Range
Hemoglobin (Female) - gm/dL	9.1 – 13.8
Hemoglobin (Male) - gm/dL	10.8 – 15.8
WBC – $10^3/\mu\text{L}$	3.6 – 9.0
Absolute Neutrophil/Granulocyte Count - $10^3/\mu\text{L}$	1.3 – 4.4
Absolute Lymphocyte Count - $10^3/\mu\text{L}$	1.3 – 4.4
Platelet Count (Female)- $10^3/\mu\text{L}$	144 – 413
Platelet Count (Male)- $10^3/\mu\text{L}$	114 – 335

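### Laboratory AEs are scored on the absolute grade with no comparison to the pre-dose value, so an unchanged Grade 1 value allowed at entry can count as a vaccine-period AE

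*Combined protocol and SAP*

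**What the plan says.** - **Definition.** Section 12.2 defines an AE to include abnormal laboratory findings associated in time with participation, "whether or not considered related to the research". It sets no condition that the finding be new or worse.
- **Collection.** Section 12.3 states that laboratory AEs as defined in Appendix D "will be collected and graded through 7 days after each vaccination or until resolved". Table 14 lists them as a class of solicited event, separate from systemic and local events.
- **Grading.** Appendix D grades absolute values only.
- **Entry.** Section 6.5, item 4, excludes "Hemoglobin, WBC, absolute neutrophils, and platelets outside the local laboratory-defined limits of normal", and item 5 does the same for ALT and creatinine. Both add that "subjects may be included at the investigator's discretion for 'not clinically significant' values outside of normal range", up to Grade 1.
- **Analysis.** Section 14.2 lists laboratory AEs with clinical ones under the primary objective and compares the share of subjects with one or more AEs. Section 14.5 applies Fisher's exact test to AE proportions, control against treated.
- **Endpoint.** Section 5.2.1 reads "Incidence of local and systemic AEs and SAEs in Malian adults. (All arms" and does not name laboratory events.
- **Available data.** Appendix C draws CBC, ALT and creatinine before doses 1 to 3 (Days 0, 28 and 168) and again 3 days after each dose.

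**The concern.** The values allowed at entry overlap the values scored as AEs after dosing. A subject admitted at Grade 1 whose result has not moved by Day 3 meets the Appendix D definition, and nothing in sections 12.2, 12.3, 12.3.1, 14.2 or 14.5 takes that result out of the count. Causality review (section 12.3.2) can call it unrelated, but it remains an AE. Where the Grade 1 edge lies at the normal limit, ordinary variation can do the same to a subject who entered with normal values.

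Section 14.1 gives estimation of AE rates as a purpose of the study. A laboratory rate that mixes carried-over and chance values with new ones overstates what follows vaccination in every arm and makes a real laboratory effect harder to see.

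**Working it through.** **1. The plan's own safety figures.** Section 14.5 gives the chance of seeing at least one serious or severe AE, 1 − (1 − p)^n. With n = 5, p = 0.275: 0.7997. With n = 10, p = 0.206: 0.9004. With n = 60, p = 0.038: 0.9022. With n = 165, p = 0.018: 0.9501. All agree with the stated 0.80, 0.90, 0.90 and 0.95. None concerns Grade 1 laboratory events.

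**2. Distance from the normal limit to the Grade 1 edge** (Appendix D): (edge − limit) / limit.

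| Analyte | Normal limit | Grade 1 edge | Distance |
|---|---|---|---|
| Platelets, male | 114 | 115 | +0.9% (overlap) |
| Haemoglobin, female | 9.1 | 9.0 | −1.1% |
| Haemoglobin, male | 10.8 | 10.5 | −2.8% |
| WBC, low | 3.6 | 3.3 | −8.3% |
| ALT | 41 | 46 | +12.2% |
| Platelets, female | 144 | 115 | −20.1% |
| Neutrophils | 1.3 | 1.00 | −23.1% |
| WBC, high | 9.0 | 11.5 | +27.8% |
| Creatinine, male | 98 | 132.60 | +35.3% |
| Creatinine, female | 72 | 97.42 | +35.3% |

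So 114-115 is both normal and Grade 1 for men, and female haemoglobin touches the limit. At the far end, male creatinine Grade 1 is "132.60 – 159.11" against a normal ceiling of 98.

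**3. One subject.** The within-subject CV of haemoglobin is not in the documents; I assume 2-5%. A reading is graded if it falls below 9.05, which rounds to 9.0 or less.

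- *True value 8.8, admitted at Grade 1.* p = Φ(0.25 / (CV × 8.8)): 0.922 at 2%, 0.715 at 5%. At least one of three Day 3 draws is graded with probability 1 − (1 − p)³, which is 98-100%. If a result counts only when its grade exceeds the pre-dose grade, the chance per draw is p(1 − p): 0.922 × 0.078 = 0.07 and 0.715 × 0.285 = 0.20. Adding rises from Grade 1 to Grade 2 gives about 7-22%.
- *True value 9.1, normal.* p = Φ(−0.05 / (CV × 9.1)): 0.392 at 2%, 0.456 at 5%. Under the worsening rule: 0.392 × 0.608 = 0.24 and 0.456 × 0.544 = 0.25.

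The rule removes most carry-over but only part of the chance crossings.

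**4. Whole population, no vaccine effect.** Simulation of 200,000 subjects, half female. Assumptions: Appendix D ranges are central 95% intervals (haemoglobin normal; WBC, neutrophils and platelets lognormal); ALT has median 18 and 97.5th percentile 41; analytes are independent; creatinine is omitted. Every Grade 1 screening value is admitted, which is the upper end of the discretion. Subjects with one or more false laboratory AEs over three Day 3 draws:

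| Within-subject correlation | As written | Grade above pre-dose only |
|---|---|---|
| 0.5 | 15% | 14% |
| 0.65 | 14% | 12% |
| 0.8 | 12% | 9% |

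The rate per dose at Day 3 is about 6%, or 3-5% if only normal values are admitted.

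**5. Effect on the comparison.** Exact Fisher power, 120 v 120, two-sided 0.05 (assumed; no level is stated for AEs), for a vaccine-caused abnormality in 10% of subjects independent of background: 44% at a 10% background (0.19 v 0.10) and 32% at 15% (0.235 v 0.15). That is about 2.3 points of power per point of background, so removing 1-3 points recovers only a few points.

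**The case against.** The best defence is that little is lost. The documents are silent on an unchanged value; they do not say it is a fresh event after each dose. Because events run until resolved, it could be recorded as one continuing event. The primary endpoint does not name laboratory AEs. AEs are tabulated by severity and relationship, Appendix D urges caution with neutropenia, laboratory halting needs Grade 2 or higher, and the main part is randomised and blinded. Section 3.5.1.1.4 reports that most pilot laboratory abnormalities were transient Grade 1 and 2 neutropenias, and neutrophils sit 23% from their limit. Finally, the worsening rule changes the simulated rate only slightly.

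All of this stands as a limit on size. It does not supply the missing rule.

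Three stronger readings are tempting and not supported:

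- *Large background.* In the earlier Mali trial (Table 2, part 2B) 31 of 50 comparator subjects, 62%, had a laboratory abnormality, and a reader might blame this mechanism and infer almost no power. That figure covers four doses and may include real illness, and that trial's grading table and entry limits are not given. The noise model gives 12-15%, not 62%.
- *Precedent in section 3.1.1.1.* The US subjects with anaemia who were low at baseline were still normal, so they moved from ungraded to graded and would count under a worsening rule too.
- *Threshold on the entry limit throughout.* This holds for female haemoglobin and male platelets; male haemoglobin is close. The general problem is entry at Grade 1.

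**Conclusion.** The plan lacks a pre-dose comparison for laboratory AEs, and its entry criteria make that matter. The size is modest: about 12-15% of subjects with a false laboratory AE over three Day 3 draws, and about 9-14% with a worsening rule. These figures rest on the assumed correlations, distributions and full use of the Grade 1 exception. The worsening rule alone would not make false events rare; getting down to 1-3% would also require confirmation at Day 14.

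In the blinded main part the excess should be the same in all arms, so it dilutes and does not bias. In pilot Arms 1a, 2a and 3a it inflates the observed rates, because section 14.6 gives them no concurrent comparator. Whether laboratory AEs belong to the primary endpoint is implied by section 14.2 but not stated in 5.2.1. The male platelet overlap is a plain inconsistency within Appendix D. The case for change rests on a clearer method at almost no cost, not on a large numerical gain.

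**What to change.** 1. In section 14.2, base the headline laboratory-AE rate and the between-arm tests on values whose grade exceeds that dose's pre-vaccination grade (Days 0, 28 and 168; for dose 4, the latest pre-dose value).
2. Add a shift table of pre-dose against post-dose grade for each analyte and dose.
3. Compare the change from pre-dose to Day 3 between arms for each analyte, adjusted for the pre-dose value. This uses the measurement itself and does not depend on where the grade edges fall.
4. State in section 5.2.1 whether laboratory AEs are part of the primary endpoint.
5. Reconcile the male platelet reference range with the Grade 1 band in Appendix D.
6. Keep every graded value in the listings and leave the halting rules unchanged.

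The cost is analysis-plan wording and one set of tables, with no new samples. The downside is slightly fewer events in the headline laboratory rate, all still visible in the listings.
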